## 5. Analysis Sets

### 5.1. All Patients Enrolled Set

The All Patients Enrolled Set will include all patients who have given informed consent/assent to this study. Unless specified otherwise, this set will be used for patient listings and for summaries of patient disposition.

### 5.2. Full Analysis Set

The Full Analysis Set (FAS) comprises all patients who have received at least 1 dose of study medication.

### 5.3. Safety Set

The Safety Set (SAF) comprises all patients who have received at least 1 dose of study medication. In this study, the SAF and FAS are coincident as no randomization occurred.

### 5.4. Pharmacokinetic (PK) Evaluation Set

The PK Evaluation Set includes all adult patients that consent to this part of the protocol and who have PK analysis performed at the 5th infusion (28-day infusion schedule) or the 7th infusion (21-day infusion schedule). The population includes all patients following the principles of the SAF for whom at least 1 concentration of total IgGs, IgG subclasses 1-4, or IgG specific antibody levels (anti-haemophilus influenza type b, anti-tetanus toxoid, anti-pneumococcal capsular polysaccharide), measured in the dense sampling period (i.e., before and after the 5th infusion of the 28-day infusion schedule and before and after the 7th infusion for the 21-day infusion schedule).

PK concentrations are listed for all patients in the PK Evaluation Set.

### 5.5. Per-protocol Set

The Per-protocol Set (PPS) includes all patients who are compliant with the study protocol without any major protocol deviations that could affect efficacy. An analysis based on the PPS will be performed for the primary efficacy endpoint as an additional supportive analysis.

### 5.6. Protocol Deviations

Deviations from the protocol will be defined in advance and documented on an ongoing basis during conduct of the clinical study based on monitoring reports (e.g., failure of eligibility criteria), data management checks, medical review and statistical programming (e.g., prohibited medications based on drug codes) and stored in the clinical study database.

Patients with major protocol deviations that affect efficacy will be excluded from the PPS based on deviations assessment in case they may have an impact on the efficacy analysis.

Major protocol deviations may include the following categories:

- Deviation from Inclusion/Exclusion criteria
- Deviations in study medication administration (infusion not administered, infusion administered late, infusion dose is <200 mg/kg or >800 mg/kg)
- Missed sampling required for dose adjustment
- Use of prohibited concomitant medications (use of other IVIG or SCIG while on trial, use of high dose oral/parenteral steroids or other immunosuppressive drugs while on trial)

This document is confidential.

- No diary data collected
- Lab results not reviewed at Screening
- Lab results related to SBI definition not completed (See Sec 8.1.1 in study protocol)
- Study visit missed

Further major protocol deviations will be defined during the Data Review Meeting (DRM) prior to database lock. Full list of major protocol deviations will be documented on the Protocol Deviation and Noncompliance Workbook.

The investigator should not implement any deviation from, or changes to the protocol, without agreement from the sponsor and prior review and documented approval/favorable opinion of an amendment from the IRB/IEC, except where necessary to eliminate an immediate hazard(s) to study patients. The investigator, or person designated by the investigator, should document and explain any deviation from the approved protocol.

This document is confidential.

## 6. General Aspects for Statistical Analysis

### 6.1. General Methods

- Unless otherwise specified, summaries will be presented for each treatment schedule (21-day and 28-day infusion schedule) and overall.
- Unless otherwise specified, continuous variables will be summarized using the number of observations (n), mean, standard deviation (SD), median, minimum, and maximum. Categorical variables will be summarized using number of observations (n), frequency and percentages of patients.
- All relevant patient data will be included in listings. All patients entered into the database will be included in patient data listings.
- Unscheduled assessments will not be included in summary tables unless specified otherwise, but will be included in the patient listings.

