## 6.9 UNSCHEDULED VISITS

During all the study periods, an unscheduled visit (non-routine study visit triggered by a specific event or for repetition of tests, e.g. Direct Coombs) may occur at Investigator's discretion and will be recorded in the source document and in eCRF.

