#### Neutropenia

A transient decrease in neutrophil count and/or episodes of neutropenia, sometimes severe, have been reported after treatment with IVIGs. This typically occurs within hours or days after IVIg administration and resolves spontaneously within 7 to 14 days.

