#### 6.2.2. Baseline

For purpose of the analysis, the baseline value is defined as the last nonmissing valid observation before the first infusion. In most cases this will be the Day 1 pre-dose value. However, if the Day 1 pre-dose value is missing or was obtained after the first infusion of study drug is administered, then the most recent value obtained prior to the initiation of study drug will serve as the baseline measurement and may be measured at an unscheduled visit.

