#### 6.4. Visit Windows

Visits will be performed every 21 ( $\pm$  3) days or 28 ( $\pm$  4) days after each infusion until week 51, or 52 (i.e., study termination visit), depending on the patient's treatment schedule. All visits will be summarized according to the nominal visit.

For PK data analysis see [Section 9.1](#).

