#### 10.4. Laboratory Evaluations

Blood chemistry, hematology, urinalysis, IgG levels, IgG subclasses and specific antibodies samples, intravascular hemolysis testing and PK blood sampling will be analyzed at a central laboratory. Direct Coombs and urine hemosiderin can be tested either centrally or at site level. The pregnancy test on urine will be performed locally at each site. This section describes the statistical analyses for blood chemistry, hematology and urinalysis. The statistical analyses for the rest of the laboratory evaluations are described in relevant [Sections 8.2.1 – 8.2.6, 9.2 and 10.7](#). Please refer also to [Table 1.1](#) and [Table 1.2](#) for the timepoints for the collection of the specimen for the laboratory tests.

The tests listed below will be performed at screening visit, at each visit before the infusion, and at the study termination visit (week 51/52):

- Blood profile:  
hemoglobin, hematocrit, RBC count, WBC count with formula, number of platelets;
- Blood chemistry profile:  
total bilirubin, creatinine, blood urea nitrogen, ALT, AST, alkaline phosphatase, lactate dehydrogenase, glucose, sodium, potassium, chloride, and calcium;
- Urinalysis (qualitative and quantitative/semi-quantitative):  
bilirubin, pH, protein, blood, nitrite, specific gravity, leukocyte esterase, RBCs, WBCs.

These safety laboratory assessments will be categorized with respect to the central laboratory reference ranges as normal/abnormal. Abnormal values will be further classified with respect to clinical relevance: not clinically significant (NCS) or clinically significant (CS). Changes over time will be described by means of “shift-tables”, comparing the post-baseline values versus baseline value. Definition of baseline is given within [Section 6.2.2](#). Absolute change and relative change from baseline are defined in 6.2.3 and 6.2.4, respectively.

The raw data will be listed. Values below or above the reference values in the data listings will be flagged. All laboratory values will be converted into standard units for presentation reasons.

The pregnancy test on urine (for patients of childbearing age) will be also performed at the screening visit. All data will be listed.

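### SAP 10.4 tabulates safety laboratory data without unscheduled post-baseline values and with shift categories that do not separate low from high, so a typical transient neutropenia would be missing from the laboratory summary tables

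*SAP*

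**What the plan says.** SAP 6.1 states: "Unscheduled assessments will not be included in summary tables unless specified otherwise, but will be included in the patient listings". SAP 6.4 adds: "All visits will be summarized according to the nominal visit".

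SAP 10.4 covers hematology, blood chemistry and urinalysis, sampled at screening, before each infusion and at termination. On classification it says: "These safety laboratory assessments will be categorized with respect to the central laboratory reference ranges as normal/abnormal". Abnormal values are then divided into not clinically significant (NCS) and clinically significant (CS). Change over time is shown in shift tables "comparing the post-baseline values versus baseline value". The section points to the definitions of absolute and relative change but does not say that change will be tabulated. It defines no worst post-baseline value and says nothing about unscheduled results. Listings flag values below or above the reference range.

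SAP 6.2.2 lets a baseline value come from outside the schedule: it "may be measured at an unscheduled visit". SAP 10.7 brings extra time points into the hemolysis summaries after a positive Coombs test.

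Protocol 6.9 describes an unscheduled visit as a "non-routine study visit triggered by a specific event or for repetition of tests". Protocol 8.2.5 lists neutropenia, hemolysis and acute renal failure among the medical events of interest. Protocol 7.1.2 says of neutropenia after IVIg: "This typically occurs within hours or days after IVIg administration and resolves spontaneously within 7 to 14 days".

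**The concern.** The scheduled samples sit at the end of each dosing interval. A test prompted by symptoms in the days after an infusion is an unscheduled visit, and the general rule keeps it out of the SAP 10.4 tables. For an abnormality that comes and goes within one interval, the scheduled samples miss it and the tables omit the samples that could catch it.

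The shift categories add a second loss. A move from normal to low neutrophils and a move from normal to high neutrophils fall in the same cell, and a move from high to low can count as no shift. For neutrophils the safety question has one direction, and this table does not show it.

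At stake is whether the laboratory tables in the study report can be read as evidence on neutropenia. A reader who sees no shift there could take it as reassurance, although the samples tabulated were not placed to detect the event.

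**Working it through.** The plan states no figure to reproduce. The check compares timings taken from the documents.

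**Inputs**
- Visits occur 21 ± 3 or 28 ± 4 days after each infusion (SAP 3.4 and 6.4; Protocol 4.1).
- Safety laboratory samples are drawn before the infusion (SAP 10.4; Protocol 8.2.3).
- Neutropenia begins within hours or days and typically resolves within 7 to 14 days (Protocol 7.1.2).

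**Earliest scheduled sample after an infusion**
- 21-day schedule: 21 − 3 = day 18.
- 28-day schedule: 28 − 4 = day 24.

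**Gap, if the 7 to 14 days run from the infusion**
- 21-day schedule: 18 − 14 = at least 4 days.
- 28-day schedule: 24 − 14 = at least 10 days.

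**Gap, if they run from onset.** The protocol does not give an onset day, so assume day 0 to day 3. The latest recovery is then 3 + 14 = day 17, still before day 18 and well before day 24. The limit of this argument is an onset on day 4 with the full 14-day course: 4 + 14 = day 18, which could coincide with the earliest sample on the 21-day schedule.

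**Scheduled post-baseline samples per completer**
- 28-day schedule: visits 2 to 13 (12) plus termination = 13.
- 21-day schedule: visits 2 to 17 (16) plus termination = 17.

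There are many samples, but all fall late in the interval, so their number does not help with a short-lived fall.

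**Is there an exception for these data?** SAP 6.1 allows one where it is specified. SAP 10.7 specifies one for the hemolysis panel after a positive Coombs test. SAP 10.4 specifies none, so unscheduled neutrophil counts and creatinine values stay out of its tables.

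**The case against.** The strongest reply is that the laboratory tables are not the sole output. Protocol 9.1.1 counts an abnormal laboratory finding as a possible adverse event, and Protocol 9.2.3 requires clinically significant abnormalities to be investigated and documented. A fall reported as an adverse event enters the tables of SAP 10.3. SAP 10.7 gives a separate, directional summary of patients with a hemoglobin drop of at least 2.0 g/dL, low haptoglobin and raised lactate dehydrogenase. SAP 10.4 refers to signed change from baseline, and the revision history says relative change was added there. Listings keep unscheduled values and show direction. Table layouts are deferred to shells that are not part of these documents.

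Much of this stands, and it rules out three stronger readings that a reader might infer:
- *Post-infusion falls would appear nowhere.* They can reach the adverse event tables, the listings, the SAP 10.7 summaries and, if they persist, the scheduled samples.
- *The planned outputs as a whole cannot tell a fall from a rise.* That is true of the shift categories as written, but not of the listings or of signed change.
- *The same blind spot is shown for hemoglobin and renal function.* The protocol gives a short recovery time for neutropenia alone, and says typically.

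Using an unscheduled value as baseline is also no contradiction: it fills in when the Day 1 pre-dose value cannot serve.

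The reply does not close the gap for neutrophils. Under Protocol 9.2.3, clinical significance is the investigator's judgment, tied to a need for physician intervention or possible seriousness. A neutropenia that resolves unaided may not meet it. Protocol 9.2.6 prefers a diagnosis to its component findings, so a laboratory fall may not be coded separately. SAP 10.5 and 10.6 commit to presenting change from baseline, whereas SAP 10.4 merely cites the definitions. Any such summary by visit would use scheduled values. Listings give no incidence.

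**Conclusion.** The point holds in limited form. As written, SAP 10.4 leaves unscheduled post-baseline values out of its tables and uses shift categories without direction. A typical transient neutropenia would be over before the next scheduled sample, by at least 4 days (21-day schedule) or 10 days (28-day schedule) if counted from the infusion. It would then be visible in listings or, if reported, as an adverse event, but not in the laboratory summaries.

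This rests on the protocol's own time course and, if recovery is counted from onset, on the assumption of onset by day 3. Slower episodes could be caught at a scheduled visit. Hemoglobin is partly covered by SAP 10.7. For renal function the documents support the lack of direction in the shift table but no timing argument. The documents give no expected frequency, so the number of patients affected cannot be estimated. The primary analysis is not touched. This is an inexpensive improvement to safety reporting that should be made.

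**What to change.** In SAP 10.4:
1. Add a shift table from baseline to the worst post-baseline value for each parameter, using scheduled and unscheduled results. State that this is an exception to SAP 6.1.
2. Classify as low/normal/high, with the lowest and the highest post-baseline values shown separately. Qualitative urinalysis items can stay normal/abnormal.
3. State that absolute and relative change from baseline will be tabulated, as SAP 10.5 and 10.6 already do for vital signs and body weight.
4. Keep the by-visit tables on scheduled values.

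The cost is SAP wording and one more table type, with no new data collection. There are two downsides. Unscheduled results from local laboratories need their own reference ranges, because SAP 10.4 classifies against the central ones. Worst values also depend partly on who was tested, so a footnote should give the number of patients who contributed unscheduled results.

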### 6.2. Key Definitions

#### 6.2.1. Age

Age (years) = floor((date of informed consent – date of birth)/365.25)

#### 6.2.2. Baseline

For purpose of the analysis, the baseline value is defined as the last nonmissing valid observation before the first infusion. In most cases this will be the Day 1 pre-dose value. However, if the Day 1 pre-dose value is missing or was obtained after the first infusion of study drug is administered, then the most recent value obtained prior to the initiation of study drug will serve as the baseline measurement and may be measured at an unscheduled visit.

#### 6.2.3. Absolute Change from Baseline

Absolute change from baseline:

Absolute change = Post-baseline value – Value at baseline

#### 6.2.4. Relative change from baseline

Relative change = [(Post-baseline value – Value at baseline) / Value at baseline] x100

#### 6.2.5. Completion

A patient will be defined as “completed” if s/he has received all intended doses of Klg10 and has completed the 3 or 4 weeks (according to the treatment regimen) safety study termination visit after the last dose of Klg10.

#### 6.2.6. Date of first infusion (Day 1)

Date of first infusion is the earliest day/time that infused Klg10 is first initiated. Day 1 is associated to this date.

This document is confidential.

6.2.7. Duration of Study

Duration of study = Date of termination – Date of first infusion + 1

6.2.8. Duration of infection

Duration of infection [days] = Date of stop of infection – Date of start of infection + 1

6.2.9. Duration of antibiotics for the treatment of any kind of infection

Duration of antibiotic treatment [days] = Date of stop of antibiotic treatment – Date of start of antibiotic treatment + 1

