### 8.1.6.2 USE OF THERAPEUTIC ANTIBIOTICS

The patient/patients' parent(s)/legal guardian(s) will also provide the information regarding the use of therapeutic antibiotics, including the duration of patient on antibiotics, for the treatment of any kind of infections in the Patient Diary that will be provided starting from the first infusion visit.

Information entered in the diary since the previous visit will be reviewed at the following visit and collected in the specific eCRF page.

Start dates and stop dates of antibiotic treatment will be collected to determine the number of days on therapeutic antibiotics.

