### 4.2. Secondary Efficacy Endpoints

1. Serum IgG trough levels before each infusion of KIG10 and at the study termination visit (week 51/52).
2. IgG subclasses levels (IgG1, IgG2, IgG3, IgG4) before infusions 1, 5, 9 and 13 for the 28-day infusion schedule, and before infusions 1, 7, 11 and 17 for the 21-day infusion schedule.
3. Frequency of patients with total IgG below 6 g/L criteria.
4. Anti-tetanus toxoid antibody level (quantitative assay) before infusions 1, 5, 9 and 13 for the 28-day infusion schedule and before infusions 1, 7, 11 and 17 for the 21-day infusion schedule.
5. Anti-pneumococcal capsular polysaccharide antibody level (quantitative assay) before infusions 1, 5, 9 and 13 for the 28-day infusion schedule and before infusions 1, 7, 11 and 17 for the 21-day infusion schedule.
6. Anti-measles antibody level (quantitative assay) before infusions 1, 5, 9 and 13 for the 28-day infusion schedule and before infusions 1, 7, 11 and 17 for the 21-day infusion schedule.
7. Anti-Hemophilus influenza type b antibody level (quantitative assay) before infusions 1, 5, 9 and 13 for the 28-day infusion schedule and before infusions 1, 7, 11 and 17 for the 21-day infusion schedule.
8. Incidence rate (i.e., the mean number per patient-year) of any infection other than acute serious bacterial infections from day 1 to week 51/52.
9. Duration of any infection other than acute serious bacterial infections from day 1 to week 51/52.
10. Incidence rate (i.e. the mean number per patient-year) of fever episodes, from day 1 to week 51/52.
11. Duration of fever episodes, from day 1 to week 51/52.
12. Overall hospitalization days from day 1 to week 51/52.
13. Days of hospitalizations due to infection from day 1 to week 51/52.
14. Incidence rate (i.e. the mean number per patient-year) of patients on antibiotics for the treatment of any kind of infection from day 1 to week 51/52.
15. Duration of patients on antibiotics for the treatment of any kind of infection from day 1 to week 51/52.
16. Days of missed work/school/other major activities due to infections from day 1 to week 51/52.

This document is confidential.

17. PedsQL™ score at baseline, week 24 (infusion 7 for the 28-day schedule and infusion 9 for the 21-day schedule), and at the study termination visit.

CCI

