6.2.17. Prior/Concomitant medication

A medication is regarded as “prior” if the stop date of the event is prior to the date of first infusion, irrespective of the start date.

The medication is regarded as “concomitant” if the start date or stop date is between the date of first infusion (included) and the day of study termination (included).

The medication is regarded as “concomitant” if ticked as ongoing on the CRF.

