##### 6.3.2.1. AEs

For missing or incomplete start dates, if the month/year is the same as the Day 1 month/year then the date will be set to the date of Day 1. In other cases, missing days will be imputed as the day component of Day 1; missing months/years will be imputed as the month/year of Day 1. Incomplete end dates are assumed to have ended on the study completion date. Actual values will be presented in data listings.

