##### 6.3.2.2. Concomitant medications:

No data will be imputed.

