#### 8.2.10. Antibiotics for the treatment of any kind of infection

The following information will be summarized for antibiotic treatment of any kind of infection between day 1 and week 51/52:

- Percentage of patients taking at least an antibiotics for treatment of infections
- Estimate of mean and SD of the incidence rate by the simple estimator
- Duration on antibiotics for the treatment of any kind of infection
- The estimate and 1-sided 99% upper confidence limit using Poisson model.

The length of the observation period after the start of treatment per patient will be used as offset in the Poisson model. The unit of measurements of time is years.

Definition of incidence rate is given in [Section 8.1.1](#).

Computation of the estimate and 1-sided 99% upper confidence limit using Poisson model is given in [Section 8.1.2](#).

Computation of the simple estimator is given in [Section 8.1.3](#).

Definition of duration of antibiotics for the treatment of any kind of infection is given in [Section 6.2.9](#).

In addition, the number and percentage of patients taking concomitant antibiotic medications will be summarized by ATC Levels 2, 3 and 4.

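### The antibiotic-duration formula in SAP 6.2.9 has no limits at Day 1 or termination, so it over-counts courses that straddle Day 1 and gives no value for courses still running at termination

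*SAP*

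**What the plan says.** Secondary endpoint 15 in SAP 4.2, matched in Protocol 10.4.1, is "Duration of patients on antibiotics for the treatment of any kind of infection from day 1 to week 51/52". Protocol 8.1.6.2 has antibiotic start and stop dates collected to "determine the number of days on therapeutic antibiotics".

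SAP 8.2.10 opens with "The following information will be summarized for antibiotic treatment of any kind of infection between day 1 and week 51/52". For the calculation it points elsewhere: "Definition of duration of antibiotics for the treatment of any kind of infection is given in" Section 6.2.9. That section reads "Duration of antibiotic treatment [days] = Date of stop of antibiotic treatment – Date of start of antibiotic treatment + 1".

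The records that enter are set by SAP 7.5, which identifies concomitant antibiotics with this endpoint, and by SAP 6.2.17. The latter calls a medication concomitant "if the start date or stop date is between the date of first infusion (included") and the study termination day, and also if it is ticked as ongoing on the CRF.

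On missing values, the default in SAP 6.3 is no replacement unless a section says otherwise. SAP 6.3.1 leaves efficacy endpoints other than the primary to their own sections, and 8.2.10 has no rule. SAP 6.3.2.2 says of concomitant medications: "No data will be imputed".

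**The concern.** The endpoint names a window and the formula ignores it. That matters for two kinds of course.

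- **Crossing Day 1.** Days on antibiotics before the first KIg10 infusion, when the patient was still under the previous IVIg, are added to a measure meant to describe time on KIg10.
- **Running at termination.** Days that truly fell on study are dropped because the course had not finished.

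The first inflates the reported duration and the second removes days from it, so the net effect is unknown. Infection-related antibiotic use is one of the few supportive efficacy measures in a single-arm trial, so its day count should match its stated period. The documents also leave two programmers free to produce different numbers from the same data.

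**Working it through.** The plan gives no target, expected value or sample-size figure for antibiotic duration, so there is nothing to reproduce first. The check applies the SAP 6.2.9 arithmetic to example courses and compares it with the same arithmetic held to the window. Course dates are assumptions, because the documents give none.

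**Inputs**
- As written (SAP 6.2.9): stop − start + 1.
- Limited to the window: min(stop, termination) − max(start, Day 1) + 1.
- Nominal termination day, counting the first infusion as Day 1: 1 + 13 × 28 = Day 365 on the 28-day schedule; 1 + 17 × 21 = Day 358 on the 21-day schedule.

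**Can a course straddle Day 1?** Yes. Exclusion criterion 8 concerns documented acute infection or fever within 7 days before screening. Screening can precede Day 1 by up to 28 days (21 on the shorter schedule). No exclusion criterion bars antibiotic use. Protocol 6.6 records prior and concomitant antibiotics at baseline, so start dates before Day 1 can be in the data. If such a course stops on study, SAP 6.2.17 makes it concomitant.

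**Courses started p days before Day 1 and stopped on Day 5.** From start to Day 5 is p + 4 days, so the formula gives p + 5. The window-limited value is always 5, and the excess is p.

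| p | SAP 6.2.9 | In window | Excess |
|---|---|---|---|
| 3 | 8 | 5 | 3 |
| 7 | 12 | 5 | 7 |
| 14 | 19 | 5 | 14 |
| 28 | 33 | 5 | 28 |

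**Courses ongoing at termination, started q days before it.** There is no stop date, so SAP 6.2.9 returns nothing. The window-limited value is q + 1.

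| q | SAP 6.2.9 | In window |
|---|---|---|
| 2 | missing | 3 |
| 6 | missing | 7 |
| 13 | missing | 14 |
| 27 | missing | 28 |

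**Course wholly inside the window, Day 100 to Day 109.** Both versions give 109 − 100 + 1 = 10 days.

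These results are the same on both schedules.

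**The case against.** The best defence is that SAP 8.2.10 states the window in words, so a careful programmer would cut courses at Day 1 and termination. That shows the intent, but the definition it cites does not carry it out. For an ongoing course, cutting also needs an end-date rule, and none is given.

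Several other points stand and limit the finding. The formula is right for every course wholly inside the window. An ongoing course does not leave the analysis altogether: SAP 8.2.10 also reports the percentage of patients on antibiotics and an incidence rate, and neither needs a stop date. The endpoint is descriptive, and neither the primary test nor any success threshold depends on it.

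A reader might infer more than the documents support:

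- **That the longest courses drop out.** What decides is whether a course is running at termination. A long course is more likely to be, but a two-day-old course at termination is lost and a long mid-study course is kept.
- **That very long pre-study courses dominate.** The screening gap explains starts a few weeks before Day 1. Long-term prophylaxis is outside an endpoint limited to treatment of infection.
- **That an ongoing infection gets a duration while its antibiotic does not.** SAP 6.3.2.1 says of AEs "Incomplete end dates are assumed to have ended on the study completion date", but this sits under safety endpoints, and the SAP does not extend it to the efficacy infection duration. SAP 6.3.2.2 sits under the same safety heading, but the default in 6.3 gives the same result for antibiotics.
- **That two drugs given together are counted twice.** SAP 6.2.9 does not say whether it works per drug, per episode or per patient, nor that records are summed. This is an ambiguity, not a shown error.

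**Conclusion.** The concern holds for two boundary cases. Applied as written, SAP 6.2.9 adds every pre-Day-1 day of a course that straddles Day 1 (3 to 28 extra days in the assumed examples) and gives no duration for a course ongoing at termination (3 to 28 on-study days lost in the assumed examples). These sizes are per course and rest on assumed dates and a literal reading of the rules. The effect on the trial's summary cannot be computed, because the documents do not say how often such courses occur. It does not follow that the endpoint as a whole is uninterpretable. This is worth correcting before database lock, at the level of a secondary descriptive endpoint.

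**What to change.** In SAP 6.2.9 and 8.2.10, define duration as min(stop, termination date) − max(start, Day 1) + 1. Set the stop of an ongoing course to the patient's termination date and flag it as censored, so that the number of such courses can be shown. Apply the same limits to duration of infection (6.2.8) and duration of fever (6.2.10) where relevant, since both use the same unbounded form.

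As a clarification, state that overlapping antibiotics are counted as distinct calendar days per patient.

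The cost is SAP wording and minor programming. Start and stop dates and the ongoing tick are already collected. The reported duration may move in either direction, and may be slightly less favourable once ongoing courses are counted.
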